**Table 11      Intervals between study visits during special circumstances**

Interval	Optimal length of interval	Allowed interval per Protocol	Allowed interval during special circumstances
Visit 1→Visit 2	60 days (2 months)	49 days - 83 days	49 days – 180 days
Visit 2→Visit 3	30 days (1 month)	28 days- 48 days	28 days- 90 days
Between Monthly Contacts*	30 days (1 month)	20 – 40 days	20 – 40 days
Visit 2→Month 26 Contact (for the last enrolled subject only)	730 days (24 months)	730- 760 days	730- 760 days

*Note: Investigator should prioritize conducting the visit as close to the optimal window as possible.*

- *Visits for suspected HZ may take place in a different location\* other than the study site or at subject's home. If this is not feasible, then the medical evaluation of suspected HZ may take place virtually with documentation of all the signs and symptoms as outlined in Table 8 and Table 10.*
  - *If the subject is not able to contact the study staff/investigator to evaluate/ clinically diagnose the suspected HZ case, the subject should be encouraged to document all the signs and symptoms and record the progression of the rash and share it with the investigator when possible.*
  - *Digital photographs can be taken by the study staff/investigator at a different location\* other than the study site or at subject's home. If this is not feasible, subjects might be asked to take photographs of their Hz lesions themselves. The photographs will be transferred to the investigator.*
  - *ZBPI questionnaire may be transmitted from and to the site by electronic means and/or conventional mail. If feasible the study staff/investigator can conduct ZBPI questionnaire by telephone contact.*

*Impact on the modified exposed set for HZ recurrence analysis and per protocol set for immunogenicity (humoral and CCI ) will be determined on a case by case basis.*

#### Section 9.3.3.4. Medically attended visits

For each solicited and unsolicited AE/SAE the subject experiences, the subject/subject's LAR/caregiver will be asked if he/she /the subject received medical attention defined as hospitalization, or an otherwise unscheduled visit *by* medical personnel for any reason, including emergency room visits.

CCI

CRF Case Report Form

CSR Clinical Study Report

CTRS Clinical Trial Registry Summary

ELISA Enzyme-linked immunosorbent assay

EoS End of study

ES Exposed Set

gE VZV glycoprotein E

[figure not shown]
GMC Geometric mean antibody concentration

GSK GlaxoSmithKline Biologicals SA

HI Humoral Immunogenicity

HZ Herpes Zoster

ICF Informed consent form

IMC	Intercurrent Medical Condition
LL	Lower Limit of the confidence interval
LSLV	Last Subject Last Visit
MedDRA	Medical Dictionary for Regulatory Activities
mES	Modified Exposed Set
NA	Not Applicable
PBMC	Peripheral blood mononuclear cells
PCD	Primary completion date
PD	Protocol Deviation
PHN	Postherpetic Neuralgia
pIMD	Potential Immune-Mediated Disease
PPS	Per-Protocol Set
SAE	Serious adverse event
SAP	Statistical Analysis Plan
SBIR	GSK's Internet Randomization System
SD	Standard Deviation
SDTM	Study Data Tabulation Model
TFL	Tables Figures and Listings
CCI	
TOC	Table of Content
UL	Upper Limit of the confidence interval
VRR	Vaccine response rate
WBR	Web-based Randomization
YOA	Years of Age

1. DOCUMENT HISTORY

Date	Description	Protocol Version
28 AUGUST 2019	First version	Amendment 1: 18 MAR 2019
24 JANUARY 2020	Amendment 1: amendment of the SAP definition of enrolled set to better align across study documents, specifically the protocol and eCRF completion guidelines. None of these modifications are major changes to planned analysis.	Amendment 1: 18 MAR 2019
06 Oct 2023	
Amendment 2:
 
The protocol was amended to include subjects vaccinated beyond the original 2-month dose interval during the special circumstances of the COVID-19 pandemic. Per CHMP Scientific Advice received on March 24, 2022, the SAP is amended to add a sensitivity analysis for non-inferiority after removing the participants who received a second dose more than 2 months after the first dose (outside of the original scheduled window), a stratified analysis for non-inferiority by recruitment interruption, and Kaplan-Meier curves to compare the onset time of HZ recurrences.
 
Added clarifications on how to handle extreme cases, when there are no confirmed HZ cases in one of the treatment groups.
 
Added analysis to assess the impact of COVID-19 on safety.
	Amendment 2: 14 APR 2020

2. OBJECTIVES/ENDPOINTS

2.1. Objectives

2.1.1. Primary objectives

- To compare the incidence of Herpes Zoster (HZ) recurrence in the HZ/su group to the placebo group

A formal non-inferiority analysis with non-inferiority margin of 5 will be performed

[figure not shown]
- *Criterion: The objective is met if the upper limit (UL) of the 95% confidence interval (CI) of the ratio of the incidence of HZ recurrence (HZ/su versus placebo) is below 5.*

2.1.2. Secondary objectives

- To evaluate the rate of HZ recurrence in HZ/su and placebo groups during the entire study period.
- To evaluate safety and reactogenicity following administration of HZ/su vaccine or placebo within 30 days after each dose.

- To evaluate safety following administration of HZ/su vaccine or placebo during the entire study period.
- To characterize anti-gE humoral immunogenicity response prior to the first vaccination (Day 1), at two months post first vaccination (Month 2) and at one month post last vaccination (Month 3) in both groups.

CCI

2.2. Endpoints

2.2.1. Primary endpoints

[figure not shown]
- Occurrence of confirmed HZ episodes from 30 days post second vaccination until study end.

2.2.2. Secondary endpoints

- Occurrence of confirmed HZ episodes from first study vaccination until study end
- Reactogenicity and safety, in all subjects
 - Occurrence, intensity and duration of each solicited local adverse event (AE) within 7 days (Days 1-7) after each vaccination.
 - Occurrence, intensity, duration and relationship to vaccination of each solicited general AE within 7 days (Days 1-7) after each vaccination.
 - Occurrence, intensity and relationship to vaccination of unsolicited AEs within 30 days (Days 1-30) after each vaccination, according to the Medical Dictionary for Regulatory Activities (MedDRA) classification.
 - Occurrence and relationship to vaccination of all serious adverse events (SAEs) from dose 1 up to 30 days post last vaccination.

- Occurrence and relationship to vaccination of any potential immune mediated diseases (pIMDs) from dose 1 up to 30 days post last vaccination.
- Occurrence and relationship to vaccination of all SAEs within the period starting after 30 days post last vaccination until 1 year post last vaccination.
- Occurrence and relationship to vaccination of any pIMDs within the period starting after 30 days post last vaccination until 1 year post last vaccination.
- Occurrence of SAEs related to investigational vaccine, related to study participation or to GSK concomitant medication/vaccine during the entire study period.
- Immunogenicity, in all subjects
 - Vaccine response for Anti-gE humoral immunogenicity as determined by Enzyme-linked immunosorbent assay (ELISA) at Month 2 and Month 3.
 - Anti-gE antibody concentrations as determined by ELISA at Day 1, Month 2 and Month 3.

CCI

[figure not shown]

CONFIDENTIAL

204939 (ZOSTER-062)

[figure not shown]
Statistical Analysis Plan Amendment 2

CCI

3. STUDY DESIGN

Figure 1 Overview of Study design

BS= Blood sampling; HZ= Herpes Zoster; N= number of subjects planned to be enrolled; Vacc= Vaccination

*A blood sample (approx. 5ml per visit) will be collected from all subjects at Visits 1, 2 and 3. An additional blood sample (approx. 20ml per visit) will be collected from subjects in the cell mediated immunity sub-cohort at Visits 1, 2 and 3.

†The duration of the study will vary for each subject. Study conclusion will be scheduled based on the projected date of the last contact of the last enrolled subject, that is 26 months (790 days) from the enrolment date. The study conclusion visit/ contact for subjects with an ongoing episode of HZ will occur after a 4-week pain-free period is documented OR after Day HZ-92 follow-up has been completed.

- **Experimental design:** Phase III, observer-blind, randomized, placebo controlled, multicenter, multi-country study with two parallel groups.
- **Duration of the study:** The duration of the study will vary for each subject. The duration of the study will be up to the study conclusion contact that occurs within 30 days of the projected study conclusion date of the last enrolled subject, that is, 26 months (790 days) from the enrolment date. Therefore, subjects enrolled early in the trial could be followed for longer duration than the subjects who enrol later in the trial. The study conclusion visit/ contact for subjects with an ongoing episode of HZ at the time of last subject last visit (LSLV) will occur after a 4-week pain-free period is documented OR after Day HZ-92 follow-up has been completed.
 - **Epoch 001:** Starting at Visit 1 (Day 1) followed by Visit 2 at two months post first vaccination (Month 2), Visit 3 at one month post last vaccination (Month 3).
 - **Epoch-002:** Starting with monthly contact after Visit 3 (Month 3) and ending at the monthly contact that occurs within 30 days of the projected study conclusion date of the last enrolled subject, that is, 26 months (790 days) from the enrolment date.
- **Primary completion Date (PCD):** The primary completion date will be when the last subject completes their study conclusion contact (within 30 days of the projected study conclusion date of the last enrolled subject, that is, 26 months [790 days] from the enrolment date).

Refer to the protocol glossary of terms for the definition of PCD.

- **End of Study (EoS):** 1) After all the subjects complete their study conclusion contact, occurring within 30 days of the projected study conclusion date of the late enrolled subject, that is, 26 months (790 days) from the enrolment date of the last subject and 2) the release of all polymerase chain reaction (PCR) test results for the HZ rash lesion sample.

Refer to the protocol glossary of terms for the definition of EoS.

- **Study groups:**

Table 1 Study groups and epochs foreseen in the study

Study groups	Number of eligible subjects	Age (years)	Epochs	
			Epoch 001	Epoch 002
HZ/su	713	≥50 years	•	•
Placebo	713	≥50 years	•	•

- **Control:** placebo controlled
- **Vaccination schedule:** 0 and 2 months
- **Treatment allocation:** Eligible subjects will be randomized (1:1) to HZ/su group or placebo group. The randomization algorithm will use a stratification procedure accounting for age (50-59 years of age [YOA]; 60-69 YOA and ≥ 70 YOA) and also a stratification procedure accounting for 'time since previous HZ episode' (≤ 4 years ago, 5-9 years ago, ≥ 10 years ago). Additional minimization factors include: (female) gender, center, family (first degree blood relative) history of HZ, history of PHN and a combined minimization factor to reflect the presence of any of the following conditions: type 2 diabetes mellitus, asthma, chronic obstructive pulmonary disease, chronic kidney disease and depression.

[figure not shown]
Table 2 Expected enrolment based on overall age stratification

Age stratum	Sample size	Percentage of total
50-59 YOA	Min 285	Min 20
60-69 YOA	Min 285	Min 20
≥70 YOA	Min 143	Min 10
All	1426	100.0

Table 3 Expected enrolment based on time from previous HZ case

Sub-group	Sample size	Percentage of total
≤4 years ago	Min 143	Min 10
5-9 years ago	Min 143	Min 10
≥ 10 years ago	Min 143	Min 10
All	1426	100.0

CCI

CCI

- **Blinding:**

Table 5 Blinding of study epochs

Study Epochs	Blinding
Epoch 001	observer-blind
Epoch-002	observer-blind

- **Sampling schedule:**

- Blood samples for humoral immunity (approximately 5 mL per visit) will be collected from all subjects at Visit 1 (Day 1), Visit 2 (Month 2), and Visit 3 (Month 3).

CCI

- Clinical specimens of HZ lesions will be collected from all subjects who are clinically diagnosed with a suspected case of HZ (Section 4.1 of the protocol).
- A urine specimen will be collected from all female subjects of child-bearing potential (see glossary of terms in protocol for definition of woman of child bearing potential) at Visit 1 (Day 1) and Visit 2 (Month 2). If a serum pregnancy test instead of a urine pregnancy test is required by country, local or ethics committee regulations, a blood sample will be collected from women of child-bearing potential at Visit 1 (Day 1) and Visit 2 (Month 2) and used for the test as per local guidance.

- **Group and sub-group information**

Table 6 Group names and description for footnote will be used in the Tables, Figures and Listings, in line with the T-domains:

Group order in tables	Group label in tables	Group definition for footnote
1	HZ/su	Subjects receiving HZ/su vaccine
2	Placebo	Subjects receiving Placebo

The following sub-groups will be used in the Tables Figures and Listings (TFL), in line with the T-domains:

Table 7 Sub-group name and definitions to be used for the sub-group analysis by age stratum

Sub-group order in tables	Sub-group label in tables	Sub-group definition for footnote
1	50-59 YOA	Subjects aged 50-59 years of age
2	60-69 YOA	Subjects aged 60-69 years of age
3	≥70 YOA	Subjects aged ≥70 years of age

YOA = Years of age

Table 8 Sub-group name and definitions to be used for the sub-group analysis by time since previous HZ episode

Sub-group order in tables	Sub-group label in tables	Sub-group definition for footnote
1	Previous HZ ≤ 4 Y	Previous HZ episode was ≤ 4 years prior to enrolment
2	Previous HZ ≥ 5 - ≤ 9 Y	Previous HZ episode was 5-9 years prior to enrolment
3	Previous HZ ≥ 10 Y	Previous HZ episode was ≥ 10 years prior to enrolment

Y = Year

4. ANALYSIS SETS

4.1. Definition

4.1.1. Enrolled Set

The enrolled set will include subjects who signed the informed consent form (ICF) and were either randomized to receive treatment or have had an invasive procedure (i.e., blood draw or vaccine administration).

4.1.2. Randomized Set

The randomized set will include subjects who signed the inform consent form (ICF) and treatment is allocated for them.

4.1.3. Exposed Set

The exposed set (ES) will include all subjects with at least one study vaccine administered.

The ES for analysis of immunogenicity will include all vaccinated subjects for whom data related to immunogenicity endpoints are available. CCI

[REDACTED]

[REDACTED]

The ES for analysis of reactogenicity (e.g., solicited AEs) will include all subjects with at least one vaccine administration documented and who have solicited safety data (i.e., symptom screen/sheet completed).

The ES for analysis of safety (e.g. SAEs) will include all subjects with at least one vaccine administered.

4.1.4. Modified Exposed Set

The modified exposed set (mES) is the primary population for HZ recurrence analysis. The mES excludes subjects from the ES who were not administered two doses of the study vaccine per protocol, or who developed a confirmed case of HZ prior to 30 days after the second vaccination.

4.1.5. Per Protocol Set for immunogenicity

The per protocol set (PPS) for immunogenicity will be defined by time-point and will include evaluable subjects from the ES:

- who meet all eligibility criteria.
- who received 2 doses of the HZ/su study vaccine or placebo according to their random assignment.
- who did not receive forbidden medications as defined in the protocol.
- who had no intercurrent medical condition (IMC) which may influence immune response.
- who complied with the vaccination schedule as specified in [Table 9](#).
- who complied with the blood sample schedule as specified in [Table 9](#).
- for whom data concerning immunogenicity endpoint measures are available.

The intervals allowed for the inclusion in the PPS for analysis of immunogenicity are defined as follows:

Table 9 Intervals between study visits

Interval	Optimal length of interval ¹	Allowed interval	Allowed interval during special circumstances ²
Visit 1→Visit 2	60 days (2 months)	49 days - 83 days	49 days – 180 days
Visit 2→Visit 3	30 days (1 month)	28 days- 48 days	28 days- 90 days

¹Whenever possible the investigator should arrange study visits according to this interval.

² Refer to protocol Section 6.7 for study procedures to be considered during special circumstances.

Based on the availability of humoral immune response result and **CCI** [REDACTED], separate PPS will be defined for humoral sample and **CCI** [REDACTED]:

- PPS-HI - all subjects meeting the criteria described above and have humoral immune result available post vaccination

CCI
[REDACTED]

For the immunogenicity tables where different timepoints are presented, the concept of “Adapted PPS for immunogenicity” will be used to denote that for each timepoint, the corresponding PPS will be used.

More specifically,

- The analyses at the Day 1 timepoint will be based on the PPS for immunogenicity Day 1;
- The analyses at the Month 2 timepoint will be based on the PPS for immunogenicity Month 2;
- The analysis at the Month 3 timepoint will be based on the PPS for immunogenicity Month 3;

4.2. Criteria for eliminating data from Analysis Sets

Elimination codes are used to identify subjects to be eliminated from analysis. Detail is provided below for each set.

4.2.1. Elimination from Enrolled Set

Code 800 (fraudulent data) and code 900 (invalid ICF) will be used for identifying subjects eliminated from Enrolled Set.

4.2.2. Elimination from Randomized Set

Code 800 (fraudulent data), 900 (invalid ICF) and code 1010 (vaccine number not allocated) will be used for identifying subjects eliminated from Randomized Set

4.2.3. Elimination from Exposed Set (ES)

Code 800 (Fraudulent data) and code 900 (invalid ICF), code 1010 (vaccine number not allocated) and code 1030 (Study vaccine not administered at all) will be used for identifying subjects eliminated from ES.

4.2.4. Elimination from modified Exposed Set (mES)

Code 800 (Fraudulent data), code 900 (invalid ICF), code 1010 (vaccine number not allocated), code 1030 (Study vaccine not administered at all), code 1050 (Randomization failure), code 1070 (Vaccination not according to protocol), code 2500 (Subject who didn't receive two doses) and code 3500 (Subject having confirmed HZ episode prior to 30 days after the dose 2) will be used for identifying subjects eliminated from mES.

4.2.5. Elimination from Per-protocol analysis Set (PPS)

4.2.5.1. Excluded subjects

A subject will be excluded from the PPS analysis under the following conditions

For codes 800, 900, 1010, 1030, 1050, 1060, 2010, 2500: subjects will be eliminated from all visits.

For codes 1040, 1070, 1080, 1090, 2040, 2050, 2080, 3500: subjects will be eliminated from a specific visit (at which the condition is met) onwards.

For code 2090: subjects will be eliminated at the specific visit at which the condition is met.

Additionally, for the PPS-HI, subjects with codes 2020, 2100, 2120 will be eliminated at the specific visit at which the condition is met. CCI [REDACTED]

Code	Condition under which the code is used	Visit (timepoints) where the code is applicable	Applicable for analysis set
800	Fraudulent data	All	All
900	Invalid ICF	All	All
1010	Vaccine not allocated	All	Randomized set, ES, mES, PPS
1030	Study vaccine not administered at all	All	ES, PPS, mES

Code	Condition under which the code is used	Visit (timepoints) where the code is applicable	Applicable for analysis set
1040*	Administration of concomitant vaccine(s) forbidden in the protocol Any concomitant vaccination not foreseen by the study protocol administered in the period starting 30 days before the first dose of study vaccine and ending at Visit 3 (Day -30 to Month 3)	Day -30 up to Month 3	PPS
1050	Randomization failure	All	mES, PPS
1060	Randomization code was broken	Day 1 to Month 3	PPS
1070**	Vaccination not according to protocol 
 • Subjects got vaccinated with the correct vaccine but containing a lower volume • Administration not according to protocol for reason specified by the investigator, other than side, site and route • Site or route of study vaccine administration wrong or unknown • Wrong replacement or 	Day 1, Month 2	mES, PPS

CONFIDENTIAL

204939 (ZOSTER-062)
Statistical Analysis Plan Amendment 2

Code	Condition under which the code is used	Visit (timepoints) where the code is applicable	Applicable for analysis set
	
study vaccine administered (not compatible with the vaccine regimen associated to the treatment number)
 
Administered study vaccine reported as being the correct one but is not compatible with the vaccine regimen associated to the treatment number
		
1080	Vaccine temperature deviation	Day 1, Month 2	PPS
1090	Expired vaccine administered	Day 1, Month 2	PPS
2010	Protocol violation (inclusion/exclusion criteria)	Day 1	PPS
2020	Unknown antibody status at pre timepoint for anti-gE humoral result (baseline sampling missing or unable to test because of hemolysis, insufficient volume)	Day 1	PPS-HI
2040*	Administration of any medication forbidden by the protocol	Day 1 to Month 3	PPS

CCI

CONFIDENTIAL

204939 (ZOSTER-062)
Statistical Analysis Plan Amendment 2

Code	Condition under which the code is used	Visit (timepoints) where the code is applicable	Applicable for analysis set
	Any concomitant medication or drug not foreseen by the study protocol (refer to section 7.7.2 of the protocol) administered in the period from the first dose of study vaccine and ending at Visit 3 (Day -30 to Month 3)		
2050*	Underlying medical condition forbidden by the protocol Any IMC (refer to section 7.8 of the protocol) which can affect the immune response to the study vaccine between the first dose of study vaccine and ending at Visit 3 (Day -30 to Month 3)	Day 1 to Month 3	PPS
2080	
Subjects who had planned study visits during special circumstances did not comply with vaccination schedule DOSE 1 - DOSE 2 = 49-180 days
 
Other Subjects did not comply with vaccination schedule DOSE 1 - DOSE 2 = 49-83 days
	Month 2	PPS
2090	
Subjects who had planned study visits during special circumstances did not comply with blood sample schedule
	Month 2, Month 3	PPS

CONFIDENTIAL

204939 (ZOSTER-062)
Statistical Analysis Plan Amendment 2

Code	Condition under which the code is used	Visit (timepoints) where the code is applicable	Applicable for analysis set
	
DOSE 1 - BS2 = 49-180 days for PPS at Month 2
 
DOSE2 - BS2 = 28-90 days for PPS at Month 3
 
Other Subjects did not comply with blood sample schedule
 
DOSE1 - BS2 = 49-83days for PPS at Month 2
 
DOSE2 - BS3 = 28-48 days for PPS at Month 3
		
2100	Serological results of anti-gE humoral not available post-vaccination	Month 2, Month 3	PPS-HI
CCI			
2120	Obvious incoherence or abnormality or error in anti-gE humoral data	Day 1, Month 2, Month 3	PPS-HI
CCI			
2500	Subjects who did not receive two doses	Month 2	mES, PPS
3500	Subjects having confirmed HZ episode prior to 30 days after the dose 2	Day 1 to Month 3	mES, PPS
CCI			

*Attribution of these elimination codes to subject need CSL review of individual listing

** Attribution of code 1070 to a subject requires CSL confirmation

PPS = PPS-HI and CCI (until specifically mentioned)

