● is used to indicate a study procedure that requires documentation in the individual eCRF.

○ is used to indicate a study procedure that does not require documentation in the individual eCRF.

 Only for women of child bearing potential. Please refer to [glossary of terms](#) for definition of woman of child bearing potential.

 Diary card to collect solicited and unsolicited AEs following each vaccination and HZ specific diary card.

 Subjects will be instructed to contact their study site immediately if he/she manifests any symptoms he/she perceives as serious and in case of pregnancy or HZ symptoms.

 Before vaccine administration

 Any subject with a clinically diagnosed suspected HZ episode between Visit 1 (Day 1) and Visit 2 (Month 2) is not to receive the second dose.

 The duration of the study will vary for each subject. Study conclusion will be scheduled based on the projected date of the last contact of the last enrolled subject, that is 26 months (790 days) from the enrolment date. The study conclusion visit/ contact for subjects with an ongoing episode of HZ will occur after a 4-week pain-free period is documented OR after Day HZ-92 follow-up has been completed.

 Refer to Section [4.5](#) and [Table 8](#) for the brief evaluation and study procedures to be followed in case of suspected HZ.

\* For the last enrolled subject only

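### SAP elimination code 2090 ties the Month 3 blood-sample window for special-circumstances subjects to BS2 instead of BS3, so on-schedule subjects cannot meet the rule as written

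*SAP*

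**What the plan says.** SAP section 4.2.5.1 lists the elimination codes that remove subjects from the analysis sets. Code 2090 covers blood-sample timing and has two branches.

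- Subjects with study visits planned during special circumstances: "DOSE 1 - BS2 = 49-180 days for PPS at Month 2", then "DOSE2 - BS2 = 28-90 days for PPS at Month 3".
- All other subjects: dose 1 to BS2 of 49 to 83 days for Month 2, then "DOSE2 - BS3 = 28-48 days for PPS at Month 3".

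The code acts visit by visit: "For code 2090: subjects will be eliminated at the specific visit at which the condition is met".

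SAP section 4.1.5 defines the per-protocol set (PPS) for immunogenicity as including those "who complied with the blood sample schedule as specified in" Table 9. For Visit 2 to Visit 3 during special circumstances, Table 9 allows "28 days- 90 days". Protocol Table 11 (section 6.7) gives the same interval.

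On the order of events at Visit 2, the footnote to the antibody blood-sampling row of protocol Table 7 reads "Before vaccine administration". Protocol Tables 7 and 16 label the Month 2 sample as taken before the second vaccination.

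**The concern.** The special-circumstances branch uses BS2 twice, once for Month 2 and once for Month 3. The Month 3 line asks for 28 to 90 days between dose 2 and a sample drawn just before dose 2, which the visit schedule rules out.

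This is an operative exclusion rule rather than background text. The PPS is the primary set for immunogenicity (SAP section 5.4.1). Month 3 seropositivity, GMC, vaccine response and fold increase are all reported on it (section 5.4.1.1.1). Vaccine response at Month 3 also requires membership of both the Day 1 and the Month 3 PPS (section 9.1.2.1).

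The branch applies to everyone with visits planned during special circumstances, whether or not they used the wider windows. A literal program would therefore drop subjects who returned within the ordinary 28 to 48 days as well as those who needed the extension. Nor does any line of code 2090, as written, check when BS3 was drawn for these subjects.

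**Working it through.** **Inputs**
- Sampling visits: Visit 1, Visit 2 and Visit 3 (SAP section 3).
- BS2 is the Visit 2 sample. The SAP does not define the label, but both Month 2 lines of code 2090 use it that way. BS3 is then the Visit 3 sample, as in the Month 3 line for other subjects.
- Dose 2 is given at Visit 2, after the blood draw (protocol Table 7).
- Special-circumstances windows: Visit 1 to 2, 49 to 180 days; Visit 2 to 3, 28 to 90 days (SAP Table 9, protocol Table 11).
- Ordinary windows: 49 to 83 days and 28 to 48 days (same tables).

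**Step 1: the interval as written.** With v2 the day of Visit 2, dose 2 to BS2 = v2 − v2 = 0 days. The condition 28 ≤ 0 ≤ 90 is false for every v2.

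**Step 2: the interval with BS3.** With g the number of days from Visit 2 to Visit 3, dose 2 to BS3 = (v2 + g) − v2 = g. The condition becomes 28 ≤ g ≤ 90, which is the Table 9 rule.

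**Step 3: all whole-day schedules that comply with the windows**

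| Windows followed | Schedules | Kept with BS2 | Kept with BS3 |
|---|---|---|---|
| Special circumstances | 132 × 63 = 8316 | 0 | 8316 |
| Ordinary | 35 × 21 = 735 | 0 | 735 |

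Here 132 = 180 − 49 + 1, 63 = 90 − 28 + 1, 35 = 83 − 49 + 1 and 21 = 48 − 28 + 1. These are counts of possible schedules, not of subjects.

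**Step 4: sample and dose on different days.** Suppose BS2 is drawn on some day from 49 up to the day of dose 2, with dose 2 on day 49 to 180. That gives 132 × 133 / 2 = 8778 pairs. The signed interval from dose 2 to BS2 is zero or negative, so none qualifies. If the interval is read as an absolute value, 4599 pairs qualify, but each requires blood drawn 28 to 90 days before the dose, which is off schedule.

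**Step 5: precision if the line were run literally.** Let f be the share of the Month 3 PPS in this category. The documents do not give f, so these values are assumptions. With unchanged variability, confidence-interval width (log scale for GMC) grows by about 1/√(1 − f).

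| Assumed f | Width factor |
|---|---|
| 5% | 1/√0.95 = 1.03 |
| 10% | 1/√0.90 = 1.05 |
| 20% | 1/√0.80 = 1.12 |
| 40% | 1/√0.60 = 1.29 |

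**The case against.** The strongest reply is that the SAP already contains the right rule. Section 4.1.5 makes Table 9 the standard for entry to the PPS, Table 9 is correct, and the neighbouring line of the code table uses BS3. A rule that no on-schedule subject can meet should show up at the first run of the program, and section 5.1.2 requires exclusions from the PPS to be tabulated. Protocol section 6.7 adds that the impact of special circumstances on the PPS is decided case by case. The endpoints concerned are secondary and descriptive.

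Most of this stands, and it limits the consequence. It does not make the line right. The code table is what identifies subjects for elimination, and code 2090 lacks the mark for individual review that codes 1040, 2040 and 2050 carry, or the confirmation step for code 1070. The case-by-case statement does not say which of two conflicting SAP rules governs.

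A reader might infer more than the documents support:

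- **That these subjects will be lost.** Loss follows only if the line is programmed literally, against the SAP's own Table 9.
- **That a head count can be given.** The share affected is not stated. Multiplying an assumed share by the enrolment target of 1426 would also overstate the loss, because the Month 3 PPS is smaller than that.
- **That the line removes exactly those whom the wider windows were meant to keep.** It reaches further, to everyone in the category.
- **That the complementary ES analysis would be triggered purely by this slip.** The 5% rule in section 5.4.1 counts exclusions for any reason. The slip could contribute to reaching it, but the ES analysis would also show the subjects dropped, since code 2090 is not an ES elimination code.

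**Conclusion.** The Month 3 line of code 2090 for special-circumstances subjects is wrong as written and contradicts SAP Table 9 and protocol Table 11. It is almost certainly a drafting slip, and the intended interval is clear: dose 2 to BS3.

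The effect is conditional. A literal program keeps none of the on-schedule subjects in this category in the Month 3 PPS, whichever window they followed; a program that follows Table 9 loses none for this reason. The conclusion assumes that BS2 is drawn at or before dose 2, as the schedule requires. The cost in precision depends on f, which is unknown.

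The Month 2 PPS is unaffected because the code is visit-specific. The mES and the primary non-inferiority test are unaffected because code 2090 is not among the mES elimination codes (SAP section 4.2.4). The point merits correction because it is an analysis-set rule, and two conflicting versions should not be left for a programmer to settle.

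**What to change.** In SAP section 4.2.5.1, code 2090, special-circumstances branch, Month 3 line, replace BS2 with BS3. The line then requires 28 to 90 days from dose 2 to BS3, in agreement with SAP Table 9 and protocol Table 11. Check that the analysis-set program uses the same interval, preferably before unblinding.

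The cost is one label in one table cell. No new data, additional analysis or change to study conduct is needed.
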